 prevent bleeding. However, platelet transfusions, due to their inflammatory nature, may
 actually worsen both bleeding and thrombosis, based on the results of the RCT in neonates
 and the observations in children on ECMO. We propose a novel composite outcome that will
 address both bleeding and thrombosis.

6. Patient Eligibility

A. Anticipated Cohort

Our aim is to enroll consecutive non-bleeding or minimally bleeding critically ill children on ECMO, who are at risk of progression to severe bleeding and/or to severe thrombosis, and at risk of receiving platelet transfusions.

Among the children on ECMO who are not bleeding on Day 1, 30% will be bleeding by Day 10 (Figure 2, page 11) (6). Furthermore, by day 10, 33% of patients will have experienced a thrombotic complication. Finally, 66% of those patients will receive at least one platelet transfusion on any given day on ECMO.

B. Criteria to Identify Participating Sites

The following criteria were used to identify participating sites in the pilot study:

1) Offering a pediatric ECMO program

2) Unanimous agreement to participate from surgical and medical practitioners (NICU, PICU, and/or CICU) and ECMO program leadership

3) Unanimous agreement to follow the PEACE anticoagulation, transfusion and hemostatic agent replacement guidelines

4) Well-established track record of excellence in clinical trials participation.

For this pilot study, there is no need for our results to be generalizable to non-study PICU groups, in terms of clinical trial experience and geographic and demographic scope. However, we will cap the number of enrolled patients per center to 10, to avoid over-representation of large centers.

In addition, as the future large RCT may require participation of **international sites**, we will include one international site in the pilot to provide some evidence on the feasibility of the trial outside of the US.

The ten participating sites are (alphabetical order): Children's Healthcare of Atlanta – Emory, Atlanta, GA; Children's Hospital of Richmond, Richmond, VA; Children's Hospital of Wisconsin, Milwaukee, WI; Duke University School of Medicine, Durham, NC; Golisano Children's Hospital, Rochester, NY; Norton Children's Hospital, Louisville, KY; Komansky Children's Hospital of New York Presbyterian, New York, NY; Morgan Stanley Children's Hospital of New York, NY; Schneider Children's Medical Center, Petach Tikvah, Israel; and University of Iowa Health Care, Iowa City, IA.

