H. Temporary suspension of Individual Patients

The protocol will allow for temporary suspensions, i.e., transfusion at a higher platelet count threshold than allowed for the randomization arm, if the clinical situation warrants immediate transfusion for certain conditions including: 1) chest-tube insertion; 2) surgical intervention while on ECMO (such as tracheostomy or repair of congenital diaphragmatic hernia); 3) during ECMO circuit change; or 4) in preparation for decannulation. In addition, while patients will be monitored for severe bleeding and/or severe clotting events during this time, they will not have the transfusion strategy permanently discontinued if they develop such an event during the temporary suspension, provided that the severe bleeding/clotting has resolved within the 24 hours of the temporary suspension. If a patient continues to have severe bleeding or severe clotting past the 24 hours of the temporary suspension, the intervention is stopped.

Adherence to the trial protocol must be resumed as soon as possible once these events are controlled or completed. Data monitoring and collection will be unchanged during suspension (including pre-transfusion platelet counts and platelet transfusion volumes), but data on length and justification of suspension will also be collected. Suspensions less than 24 hours will not be considered a breach of adherence to the protocol. After 24 hours of temporary suspension, the patient will have all assigned treatment strategy implications lifted (i.e., no restrictions on the range at which any subsequent platelet transfusions may occur) but will continue to be followed for ascertainment of safety and study outcomes. Temporary suspensions will only necessitate exclusion from analyses for one of the secondary endpoints (#6: proportion of compliant platelet transfusion actions), as explicitly noted in Section 9.B. The safety outcomes will still be followed but will be analyzed as a sub-group (e.g., severe bleeding during temporary suspensions).

9. Outcomes

The objective for the **pilot study** will be to assess the **feasibility** of the full RCT.

A. Primary Outcome

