In addition, we will measure the effect of the days on ECMO, by providing summaries of the daily platelet counts for each specific ECMO day with \geq 5 patients still on ECMO, independent of receiving a platelet transfusion. This will allow evaluating trends over time and a possible attenuation of the separation over time.

Furthermore, we will also estimate the difference in the *median platelet transfusion dose* (in mL/kg/run) between the lower and higher platelet threshold strategy arms, and the median daily platelet transfusion dose (in mL/kg/day) to account for different lengths of ECMO runs. These outcomes will use two-sided nonparametric percentile bootstrap 95% confidence intervals, based on a minimum of 10,000 bootstrap replicates, for the difference in medians because by construction for each of these outcomes, there is only one outcome per person. As such, repeated measures modeling is not warranted.

Finally, we will also report the *screening and inclusion rates*, the proportion of patients who were *approached* within 24 hours of cannulation, the proportion of patients for whom we will be able to obtain *informed consent*, the number of *platelet transfusions prior to randomization*, the proportion of compliance with *transfusion thresholds*, number of *temporary suspensions*, and the ability to record data and *adjudicate bleeding and/or clotting outcomes*. In short, we will provide summaries of outcomes, with special emphasis for these summaries on the ten feasibility criteria of Aim 2.

Unless stated otherwise, the outcomes mentioned throughout the protocol are not intended to be tested for significance in this trial, but rather will be summarized descriptively (e.g., frequency and percentage for categorical variables, means and standard deviations or medians and interquartile ranges for continuous variables).

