7.2 Primary Outcome Analysis

For the pilot study, the analysis of the primary outcome measure will be assessing the pretransfusion platelet count to describe the separation between the two platelet transfusion strategies, while accounting for intra-subject correlation. For each arm, we will estimate the mean pre-transfusion platelet count from randomization to the permanent discontinuation of the treatment strategy. This primary outcome will be measured for each transfusion and represent the latest available collected platelet count that is before the transfusion began and not before a prior transfusion. In the event that there was no preceding platelet count since a previous transfusion, the outcome for that transfusion will be regarded as missing. Participants who do not have a nonmissing value for this outcome (e.g., they had no transfusions) will not be included in the analysis of the primary outcome. Thus, the primary outcome uses all transfusions with non-missing pre-transfusion platelet counts during the period between randomization and the final termination of the transfusion strategy being in effect (whether or not during a temporary suspension) from all ITT patients with at least one such transfusion having a non-missing pre-transfusion platelet count.

7.2.1 Primary Analysis for Aim 1

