7.2.2 Additional Analyses

We will measure the effect of the days on ECMO, by providing summaries of the daily platelet counts for each specific ECMO day with ≥ 5 patients still on ECMO, independent of receiving a platelet transfusion. This will allow evaluating trends over time and a possible attenuation of the separation over time. The raw summaries for such days will be reported. As another analysis we will fit a linear model with a main linear effect for study day, a main effect for assigned treatment, a treatment by time interaction effect, and the best-fitting covariance structure, per AIC, among compound symmetry, CAR(1), the CS/CAR(1) hybrid, and subject-specific random intercepts and random time slopes. A two-df Wald test with Kenward-Roger denominator df and REML estimation will be conducted for the null

hypothesis that both the treatment main effect and the treatment by time interaction effect are 0. If this test is rejected at $\alpha = 0.05$, the interaction effect will be separately tested with a two-sided alternative at $\alpha = 0.05$. Then, if the 2-df test was significant but the 1-df test of the interaction effect was not significant, the main effect of treatment will be tested against a two-sided alternative at $\alpha = 0.05$.

Furthermore, we will also estimate the difference in the median platelet transfusion dose (in mL/kg/run) between the lower and higher platelet threshold strategy arms, and the median daily platelet transfusion dose (in mL/kg/day, i.e., $24 \times mL/kg/hr$) to account for different durations of treatment strategies. These outcomes will use two-sided nonparametric percentile bootstrap 95% confidence intervals, based on a minimum of 10,000 bootstrap replicates, for the difference in medians because by construction for each of these outcomes, there is only one outcome per person. As such, repeated measures modeling is not warranted.

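### The day-by-day check on separation pools children on and off their assigned strategy, so it may show fading when on-strategy separation is constant

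*Combined protocol and SAP*

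**What the plan says.** - SAP 7.2.2 summarises "daily platelet counts for each specific ECMO day with ≥ 5 patients still on ECMO, independent of receiving a platelet transfusion". Protocol 10.C has the same analysis: "we will measure the effect of the days on ECMO, by providing summaries of the daily platelet counts". Both give attenuation of separation as the purpose: "This will allow evaluating trends over time and a possible attenuation of the separation over time".
- SAP 7.2.2 adds a model: "we will fit a linear model with a main linear effect for study day, a main effect for assigned treatment", plus a treatment-by-time interaction. A two-df test at 0.05 comes first, and the interaction is tested only if that rejects. Neither the response variable nor the days that enter the model are stated.
- The primary outcome has a different window. SAP 7.2 takes it "during the period between randomization and the final termination of the transfusion strategy being in effect". SAP 5.5 also ends the dose outcomes at permanent discontinuation.
- The strategy can end while the child stays on ECMO. Protocol 8.G and SAP 2.2.5 list severe bleeding or clotting, 21 days, a suspension of more than 24 hours, and withdrawal. For a long suspension, protocol 8.H spells out the result: "no restrictions on the range at which any subsequent platelet transfusions may occur".
- SAP 5.2 removes data after withdrawal from the study intervention. It sets no cut-off for the other ways a strategy can end.
- The documents differ on how long daily data run. Protocol 11.A collects them throughout the ECMO run. The participation-duration entry in the protocol abstract ends daily follow-up 24 hours after the strategy expires.

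**The concern.** The useful question is whether the thresholds keep the arms apart for as long as they are applied. The stated set answers a mixed question. Suppose a strategy ends on day 4 and the child stays on ECMO to day 14. If counts continue, that child can contribute ten days with no assigned threshold. A falling curve could then mean that the strategies lose their effect, or only that fewer of the children shown are still under one.

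Separation is the pilot's primary objective (protocol 9.A). A reader who takes termination for fading could revise the full trial's treatment duration or adherence plans for the wrong reason.

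**Working it through.** **1. The plan's related figure.** No figure is given for the attenuation analysis. The nearest is the 81% power in SAP 8: difference 30, SD 40, effective sample size 30 per arm, one-sided alpha 0.025. The standard error is 40 × √(2/30) = 10.33, and 30/10.33 = 2.905. The normal approximation gives Φ(2.905 − 1.960) = 82.8%; the noncentral t with 58 df gives 81.5%. The figure is reproduced.

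**2. Inputs for the illustration.**
- On-strategy separation: 30 on every day. Protocol 10.A gives this for pre-transfusion counts; using it for daily counts is an assumption.
- Share off strategy by day 10: protocol 6.A expects 30% bleeding by day 10 and says "Furthermore, by day 10, 33% of patients will have experienced a thrombotic complication". Combined as independent, these give 1 − 0.70 × 0.67 = 53%. Protocol Appendix A gives 65% for severe bleeding, severe clotting or death, with no time point.
- Assumed: a constant rate of strategy end, unrelated to arm or to leaving ECMO.
- r, the fraction of separation that persists off strategy: not in the documents, so varied from 0 to 1.

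**3. Apparent separation if counts run to ECMO end.** With h = −ln(1 − F)/T, the off-strategy share on day d is f(d) = 1 − exp(−h·d). The apparent separation is 30 × [1 − f(d)(1 − r)]. For F = 30% by day 10 and r = 0, day 10 gives 30 × 0.70 = 21.0.

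| Off strategy | Day 10, r = 0 | r = 0.5 | r = 1 |
|---|---|---|---|
| 30% by day 10 | 21.0 | 25.5 | 30 |
| 53% by day 10 | 14.1 | 22.0 | 30 |
| 65% by day 10 | 10.5 | 20.2 | 30 |
| 65% by day 21 | 18.2 | 24.1 | 30 |

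**4. Treatment-by-day slope.** Trials of 50 children were simulated with SD 40, within-child correlation 0.3, 95% off ECMO by day 21 and constant on-strategy separation of 30. A random-intercept model was fitted, with 200 to 300 runs per cell. A Wald z test at 0.05 replaced Kenward-Roger and was applied without the preceding two-df test. The daily count was taken as the response.

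| Days used | Slope per day | Interaction rejected |
|---|---|---|
| All on ECMO, r = 0 (30%, 53%, 65% by day 10) | −0.81, −1.21, −1.40 | 17%, 27%, 34% |
| All on ECMO, r = 0.5 | −0.46 to −0.73 | 7–15% |
| All on ECMO, r = 1 (53% case) | 0.08 | 3.5% |
| On-strategy days only | 0.02 to 0.24 | 4–5% |

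**5. If counts stop 24 hours after the strategy ends.** The off-strategy share among observed children is 1 − exp(−h), or 3.5%, 7.3% and 10.0% for the three day-10 cases. The apparent separation is then 28.9, 27.8 and 27.0 on every day. It is slightly low but does not fade. The simulated slope (53% case, r = 0) is −0.24 with 5% rejection. A repeat with 1,500 runs and variance components fixed at their true values gave −0.40 and 6.5%, so the slope is only roughly known, but the rejection rate stays near nominal.

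**The case against.** A reader might infer that this analysis is bound to show fading. The documents do not support that.

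- **Data window.** The effect needs counts well beyond the end of the strategy. Under the abstract's 24-hour limit it is small (step 5). This stands, and the conflict with protocol 11.A needs resolving in any case.
- **Persistence.** Nothing in the documents says how much separation remains after a strategy ends. If all of it remains, there is no artefact. This stands.
- **The model.** It sits under the primary outcome analysis, uses study day rather than ECMO day, and draws on the same covariance candidates. It may therefore be meant for pre-transfusion counts, whose window already ends at discontinuation. This is a fair reading, but the SAP does not say so.
- **Inputs.** The 30% and 33% are not limited to severe events, and only severe ones end the strategy. The 65% includes death, which also ends ECMO. Protocol 5.A reports that bleeding is associated with time to death, so a steadily rising off-strategy share is an assumption. Daily counts may also include those drawn two to four hours after a transfusion (protocol 8.A). All of this stands; the sizes are illustrative.
- **Importance.** SE1 uses the SAP 7.2.1 model, and SAP 5.3 treats other feasibility tests as supplementary or exploratory. Attenuation over days is not among the items that protocol 10.A lists as informing the full trial. Even with r = 0, most simulated trials do not reject. This limits the weight of the point.
- **Legitimacy of the all-ECMO view.** It describes everyone by assigned arm. On-strategy days are selected by freedom from severe events after randomization, possibly differently by arm. This stands and argues for showing both.

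One thing remains after these objections. The daily summaries are descriptive, carry an explicit attenuation purpose, and use a set that cannot separate fading from termination.

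**Conclusion.** The concern holds as a possibility, not a certainty. As written, the daily summaries include every child still on ECMO, on strategy or not. They may show fading under constant on-strategy separation if two conditions are met: counts continue well past the end of the strategy, and separation shrinks once the threshold no longer applies.

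Under the assumptions in the working, a true separation of 30 would appear on day 10 as about 21 to 10.5 with no persistence and about 25.5 to 20 with half. The matching slopes are about −0.8 to −1.4 and −0.5 to −0.7 per day. With full persistence there is no effect. The rejection rates apply only if the model uses daily counts over all ECMO days, which the SAP does not state. Because the SAP also requires the two-df test to reject first, its own procedure can reject no more often than the same interaction test applied alone.

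The primary test, SE1 and the 81% power do not depend on this analysis. It is a cheap improvement to a supporting analysis.

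**What to change.** In SAP 7.2.2 and protocol 10.C:

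1. Base the attenuation summaries on counts from randomization to permanent discontinuation, indexed by study day. Print the number on strategy per arm and day; the five-patient minimum is a total over both arms, so per-arm numbers are needed to read each day.
2. Name the response variable of the treatment-by-day model and give it the same window.
3. Keep the summary over all days on ECMO as a second display, labelled as including days after the strategy has ended.
4. Reconcile the protocol abstract with protocol 11.A on how long daily counts are collected.

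The cost is one filter on dates already recorded, one more display and a few sentences. Fewer late days will be shown, and the on-strategy set is itself selected by outcome events, which is why both displays are kept.

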Subjects will be **stratified by age** (≤28 days vs >28 days) because it is infeasible to stratify by more than one variable given the sample size. We prioritized this variable since most of the safety concerns are around lower transfusion strategies in infants. Other variables considered for stratification in the future large trial will be type of ECMO support (V-A vs V-V) and site.

Patients will not be stratified based on the severity of the disease, as all scores predicting outcome on ECMO use data from the first few days of the ECMO run (43–45). In addition, scores that evaluate severity at admission (PRISM III and PIM2) are not validated nor calibrated in ECMO patients (46,47). In the pilot, we will neither stratify according to the indication (medical vs post-surgical), as this would significantly increase the sample size. However, this may be explored in regression models and sensitivity analyses.

Research personnel at each site and PICU caregivers will not have access to the randomization schedule. Moreover, in order to **conceal randomization**, 3 sizes of **blocks permutation** will be used on a random sequence: 2, 4 and 6 subjects per block.

F. Blinding

This is an open-label trial, since the **transfusion strategy cannot be blinded** from the clinical team, as they must order the transfusions based on the platelet count. The research team ([name], [name], and members of the steering committee) will be blinded to treatment allocation until the end of the analysis. Since the statisticians will need to report to the Data Safety Monitoring Board, they will not be blinded.

G. Treatment Period and Follow Up

The intervention will be implemented immediately upon randomization and maintained in effect until four possible events (whichever occurs first):

- progression to severe bleeding, according to the BASIC definition, and/or severe clotting, according to the NHLBI consensus definition, outside of temporary suspensions
- 2) decannulation from ECMO (or ECMO flow stopped, even if cannulas left in place)
- twenty-one days post-randomization (as the progression to new bleeding and new thrombosis has plateaued by day 21 and 95% of the patients will be off ECMO by then (6))
- 4) or temporary suspension lasting more than 24 hours.
- 5) Withdrawal from the study, either by the attending physician or the parents.

The mortality follow-up will be at 28 (+/- 4 days) and 90 (+/- 10) days after randomization.

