2.2.4 Additional Outcome(s)

Additional outcomes mentioned in the protocol include the following, which include most of the measures recommended in [1].

- Hemorrhagic complications according to the ELSO definition
- Thrombotic complications according to the ELSO definition
- Blood product exposure, defined as the total number of transfusions (red blood cell, plasma, platelets, cryoprecipitate, fibrinogen concentrate) and other hemostatic therapies (activated Factor VII, tranexamic acid, aminocaproic acid, DDAVP, and von Willebrand factor, etc.)
- Re-explorations and other surgical procedures to treat bleeding
- Duration of ECMO, defined as 90-day ECMO-free days (e.g., if a patient is decannulated after 7 days, the 90-day ECMO-free days is 83 days; whereas if a patient dies on ECMO after 7 days, the 90-day ECMO-free days is 0 days)
 - This is defined based on calendar days for days 1–90, with day 1 being the day of randomization and day 90 being 89 calendar days after randomization, and because every randomized patient will be on ECMO on day 1, the range for this outcome is 0–89
- Length of Pediatric Intensive Care Unit (PICU) stay, defined as the 90-day PICU-free days (as with ECMO-free days, using calendar days and with possible range of 0–89)
- Discharge Pediatric Overall Performance Category (POPC)
- Discharge Pediatric Cerebral Performance Category (PCPC)
- Mortality on ECMO
- Mortality within 24 hours of the treatment strategy being permanently discontinued
- Mortality at 28 days (obtained on or after 28 days after randomization, unless known death before)
- Mortality at 90 days (obtained on or after 80 days after randomization, unless known death before)
- Number of temporary suspensions of the transfusion strategy

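### SAP 7.2.2 does not say that the treatment-by-time term is dropped or study day centred before the treatment main effect is tested, so read literally step three tests the fitted separation at day 0

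*Combined protocol and SAP*

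**What the plan says.** After planning raw "summaries of the daily platelet counts for each specific ECMO day", SAP 7.2.2 adds a linear model with "a main linear effect for study day, a main effect for assigned treatment, a treatment by time interaction effect" and a covariance structure chosen by AIC. The tests run in three steps, each at 0.05:

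1. A 2-df Wald test that the treatment main effect and the interaction are both zero.
2. If step 1 rejects, a two-sided test of the interaction.
3. If step 1 rejects and step 2 does not, "the main effect of treatment will be tested against a two-sided alternative".

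No other mean model is given. The section does not mention a refit without the interaction, centring of day, or how day is coded. It also does not name the model's outcome. The sentences just before it concern daily counts regardless of transfusion, while the parent section 7.2 concerns pre-transfusion counts.

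The only day numbering in the SAP is in section 2.2.4, for the 90-day free-days outcomes, "with day 1 being the day of randomization". The stated reason for looking at time is "possible attenuation of the separation over time".

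**The concern.** Step three is reached when no time trend has been shown. Its natural purpose is to conclude that the arms are separated by a common amount. In a model that still contains treatment by day, however, the treatment coefficient is the arm difference at the point where day equals zero. With day uncentred, that point is at or before the start of the data, where the fitted line is less certain than in the middle.

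With about 25 patients per arm, a non-significant interaction is weak evidence that separation is constant. A separation that builds up, or one that fades, can therefore pass step two, and step three would then report a figure that is too small or too large as a summary of the separation. The choice between the literal test and a refit would also be made after the data are seen.

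**Working it through.** **The plan's own figure.** SAP section 8 gives an effective 30 independent observations per arm, SD 40 and difference 30 (all counts ×10⁹/L). SE = 40 × √(2/30) = 10.33, and 30/10.33 = 2.90. Power is Φ(2.90 − 1.96) = 83% by the normal approximation and 81.5% by the noncentral t with 58 df. The stated 81% reproduces. It belongs to the 7.2.1 test; no power is stated for the 7.2.2 model.

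**What the coefficient means.** Fitted separation at day d = β_tmt + β_int × d, so β_tmt is the separation at d = 0. It equals the separation on every day only if β_int = 0. With the day of randomization coded 1:
- Attenuation from 30 by 1.5 a day is 30 − 1.5(d − 1) = 31.5 − 1.5d. The tested value is 31.5; at a mean observed day of 6.0 the separation is 31.5 − 9.0 = 22.5.
- Growth from zero by 3 a day is 3(d − 1) = −3 + 3d. The tested value is −3; at a mean day of 6.1 the separation is −3 + 18.3 = 15.3.

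**Size.** From the documents: 25 per arm, SD 40, compound symmetry with correlation 0.3, strategy capped at 21 days. Assumed, because the documents do not give them: one count per day, geometric time on strategy, day of randomization coded 1, and the time patterns below. Expected generalised least squares coefficients for a mean of 7 days, with two-sided 0.05 power in brackets:

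| True separation | Coefficient at day 0 | At mean observed day | Interaction removed |
|---|---|---|---|
| Constant 30 | 30.0 (92%) | 30.0 (96%) | 30.0 (97%) |
| Zero on first day, then 30 | 17.9 (52%) | 24.4 (87%) | 22.7 (83%) |
| Rise to 30 over 3 days | 10.1 (21%) | 20.8 (74%) | 17.9 (63%) |
| Linear growth, 3 a day from zero | −3.0 (6%) | 15.3 (49%) | 10.4 (27%) |
| Attenuation, 30 to 0 over 20 days | 31.5 (94%) | 22.4 (80%) | 25.0 (89%) |

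For constant separation the SEs are 8.9, 7.9 and 7.8, so for example Φ(30/8.9 − 1.96) = Φ(1.41) = 92%.

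**Mean of 8 days, day 0 against refit:**
- Constant separation: SE about 8.7 against 7.6. At 30, Φ(3.45 − 1.96) = 93% against Φ(3.95 − 1.96), which is 97 to 98% given the rounding.
- Zero on the first day, then 30: about 19 against 23.5.
- Exponential rise to 30 with a time constant of 2 days: about 10 against 18.
- Attenuation: about 31 against 24.
- Simulated trials that reach step three: about 78% against 99% significant for the one-day delay, and about 50% against 94% for the exponential rise.

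**Range.** Over assumed mean stays of 5, 7 and 10 days, first day coded 0 or 1, and counts on all days or on a random 68% of days (the share of ECMO days with a platelet transfusion in protocol section 5.B), the day-0 coefficient is 30 for constant separation, 14 to 21 for the one-day delay, 6 to 15 for the 3-day rise, about −3 to 0 for linear growth from zero, and 30 to 31.5 for attenuation.

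**The case against.** **A refit may be intended.** Testing the interaction first and the main effect only if it is not significant is often shorthand for moving to a reduced model. The SAP is silent, so this cannot be excluded. But the 2-df null is stated on the main effect of the single specified model, and the same term is named in step three. The literal reading is therefore the same coefficient, and the ambiguity stands.

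**A reader might infer that randomization makes the tested quantity about zero.** The documents do not support that. Randomization balances the counts at baseline, whereas this coefficient is the intercept difference of a straight line fitted to later days. It is near zero only if separation grows roughly linearly from zero, which no passage predicts. The outcome is also unnamed. If it is the pre-transfusion count, the thresholds can separate the arms from the first transfusion: "The intervention will be implemented immediately upon randomization" (protocol section 8.G).

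**A reader might also infer that the trial could report no separation when the arms are clearly apart.** That is too strong. Step three follows a significant 2-df test, so a difference has already been declared, and the raw daily summaries are reported as well. Average pre-transfusion separation is tested in SAP 7.2.1 and judged in SE1 from a model without day or interaction. SAP 5.3 gives that test the key p-value and treats other feasibility tests as secondary in standing. Protocol section 10.C plans only the daily summaries here.

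**The literal test is not always worse.** Under attenuation, the one trend the documents name, it has more power (94% against 89% in the table). That objection is fair on power, but the power comes from a value above the average separation.

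**Conclusion.** The point holds as a minor one. Followed literally, step three tests an uncentred day-0 contrast and not the common or average separation it is placed to assess. Under constant separation nothing is biased and the cost is a few points of power at the planned difference of 30. Under non-constant separation the error can go either way: too low if separation builds up after randomization, too high if it attenuates. These sizes rest on the assumed stay distribution, daily sampling and time patterns, none of which the documents give; the direction follows from the algebra alone. No feasibility criterion, primary test or safety rule depends on this model.

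**What to change.** In SAP 7.2.2, state for step three either that the model is refitted without treatment by time under the same covariance structure and that coefficient is tested, or that the treatment contrast is tested at the mean observed study day (equivalently, that day is centred there). In the same place, name the model's outcome (daily count or pre-transfusion count) and define study day, including the value given to the day of randomization.

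The cost is one or two sentences, with no new data and no effect on sample size. Adjusting the model for the last platelet count before randomization is an optional design choice and not part of this correction.
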